8.3.5 Efficacy Analyses

All results will be interpreted in a descriptive manner, since the study is not powered to compare the treatment groups for the efficacy assessments.

For each phase (delayed, acute, and overall), numbers and percentages (including 95% CI) of patients with CR, with no emetic episodes and no rescue medication will be summarized by treatment. The difference in response rate between the groups and relevant 95% CI will be provided as well.

Efficacy analysis will be presented for the overall population and by strata.

8.3.6 Pharmacokinetic/Pharmacodynamic Analysis

PK/PD relationships between predicted individual exposure metrics (C_{max} and AUC) of netupitant versus efficacy (CR delayed phase) will be investigated via graphical exploratory analyses. In addition, a logistic regression analysis will be used to link the exposure metrics (C_{max} , AUC) to categorical response (CR delayed phase).

The dose-exposure relationship and the PK/PD correlation (exposure-response relationship) for netupitant in pediatric cancer patients will be compared to that observed in adult cancer patients in order to support the dose selection for netupitant in the pediatric population. Similar exposures in adult and pediatric patients are assumed to produce similar efficacy.

8.3.7 Safety Analyses

All AEs will be listed by SOC, described and summarized by frequency tables. Summaries will be made by treatment arm with respect to the percentage of patients having at least one occurrence of that event during the study and the total number of events.

For safety analysis, the laboratory data will be analyzed and described as follows: listings (including flag for values outside the normal range), count (number and percentage) of value below, within and above normal range, descriptive statistics for change from baseline values. Shift tables with respect to normal range (Low/Normal/High) will be presented. ECG data will be summarized highlighting differences from baseline for quantitative variables and frequencies of treatment emergent abnormalities. Vital signs will be summarized using descriptive statistics for observed values and change from baseline, in addition to being listed.

Safety analysis will be presented for the overall safety population and by strata.

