Prior and concomitant medication recording	X	X	X	X	X
Adverse event monitoring ⁸	X	X	X	X	X
PK sampling ⁹		X	X	X	

- 1 Only if applicable (for non-naïve patients).
- 2 ECOG status will be assessed for patients aged \geq 10 years.
- Whole blood, serum and urine samples will be sent to a central laboratory. Urine sample will be obtained only if the patient is capable of providing a urine sample. At the final visit (Visit 4) only, serum sample will also be used for pregnancy test.
- For female patients having reached menarche only. If screening is performed on Day -1, it is not necessary to repeat the test on Day 1.
- 5 12-lead ECG (single recording) will be evaluated in a central reading facility.

- 6 Study drugs will be administered as follows:
 - Netupitant will be administered based on the body weight as a single oral dose 1 h (± 10 minutes) prior to the start of emetogenic (HEC or MEC) chemotherapy on Day 1.
 - Oral palonosetron will be administered based on weight immediately (within 5 minutes) after netupitant, i.e., 1 h (± 10 minutes) prior to start of emetogenic (HEC or MEC) chemotherapy on Day 1.
 - Any LEC or minimally emetogenic agent given, as part of the aforementioned chemotherapy regimens using HEC or MEC, is allowed at any time during the study and does not have any impact on the time of study drugs administration
- The patient will be instructed to bring the diary back to the site at each visit so that the Investigator is able to ensure it has been completed in a timely and appropriate manner.
- 8 Starting at the screening visit, immediately after informed consent/assent, up to the follow up visit/telephone contact.
- 9 A single blood sample will be collected from each patient in each of the following time windows:
 - Pediatric patients ≥ 5 years: from 2 to 8 h, from 24 to 48 h, from 72 to 96 h, and from 120 to 168 h after netupitant administration.
 - Pediatric patients < 5 years: from 2 to 8 h, from 24 to 48 h, and from 120 to 168 h after netupitant administration.

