5.2 Study Procedures by Time Point

5.2.1 Visit 1 (screening, Day -14 to -1 or Day -7 to -1 for patients aged < 2 years)

If the Investigator considers a patient to be potentially eligible for the study, the written informed consent/assent for participation in the study must be obtained before any study-related procedures. The patient will be screened within 14 days (or within 7 days for patients aged < 2 years) prior to the first study drug administration and the following procedures will be performed/data collected during this visit:

- Informed consent signed by parent(s)/legal guardian(s) of the pediatric patient in compliance with the local laws and regulations. In addition signed children's assent form according to local requirements. Informed consent/assent may also be collected before Visit 1.
- Eligibility criteria.
- Demographic data (gender, race, date of birth).
- Medical and surgical history (including current cancer history and naivety to chemotherapy).
- History of nausea and vomiting in previous chemotherapy (if applicable).
- Prior and concomitant medications.
- Laboratory tests, including: hematology, serum chemistry and urinalysis. Urine samples will be obtained only if the patient is capable of providing a urine sample.
- Urine pregnancy test (for female patients having reached menarche only).
- Full physical examination.

- Vital signs (pulse rate, systolic and diastolic blood pressure), height/length, weight.
- 12-lead ECG (single recording).
- AE recording.
- ECOG PS (assessed for patients aged ≥ 10 years).
- Instruction to patient and to parent(s)/legal guardians of the pediatric patient on how to fill in the patient diary.

Based on the outcome of the assessments, the Investigator will be able to decide if the patient is eligible for the study.

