7 ADVERSE EVENTS

7.1 Method of Assessment

7.1.1 Definition of Adverse Events

Adverse Event (AE)

As defined by the current ICH Guideline for Good Clinical Practice [27] an Adverse Event (AE) is:

Any untoward medical occurrence in a patient or clinical investigation subject administered a pharmaceutical product and which does not necessarily have to have a causal relationship with this treatment. An AE can therefore be any unfavorable and unintended sign (including an abnormal laboratory finding), symptom, or disease temporally associated with the use of a medicinal (investigational) product, whether or not considered related to the medicinal (investigational) product.

Within the scope of this study, such untoward medical occurrences would be considered as "AEs" even if the subject was not administered the study drugs but the subject (and/or subject's parent/guardian, as applicable) had already signed the Informed Consent/Assent Form.

This definition includes intercurrent illnesses or injuries, exacerbation of pre-existing conditions, and adverse events occurring as a result of drug withdrawal, abuse, medication errors, misuse or overdose. Adverse events observed during all periods of a clinical trial are to be recorded, including adverse events occurring during a period without trial medication.

Planned surgical interventions or planned hospitalizations scheduled prior to the Informed Consent but performed during the study should not be considered (serious) AEs.

Signs and symptoms considered as lack of efficacy (nausea and vomiting) and occurring during the study up to 5 days after the study drugs administration, will not be recorded on the AEs section of the eCRF, except on the condition that, in the investigator's opinion, nausea and vomiting are caused by any reason different from lack of efficacy of study drug or meet the definition of serious AE.

Serious Adverse Event (SAE)

A serious adverse event is any event that suggests a significant hazard, contraindication, side effect, or precaution, whether or not it is considered to be associated with the study product. A SAE is an AE that meets any of the following criteria:

- Results in death. This includes any death that occurs during the conduct of a clinical study, including deaths that appear to be completely unrelated to the study drugs (e.g., car accident).

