7.1.3 Reporting of Adverse Events

AE reporting has to be in accordance with the ICH E6 Guidance on GCP and ICH E2A Guidance on Clinical Safety Management. [27, 29]

During the course of the study, all AEs (including SAEs), irrespective of the relatedness to the study drugs, will be recorded in detail in the source records and transcribed onto the AEs pages of the eCRF. During each monitoring visit, the site monitor will review all AEs and perform Source Data Verification (SDV). The investigator will be responsible for ensuring that the correct information concerning all AEs is entered on the appropriate eCRF pages.

The reporting period for AEs is the period starting from the time of Informed Consent Form signature and lasting until Visit 5 or up to 14[+3] days post-dose. All non-resolved AEs (including SAEs) beyond this date will be documented on the eCRF as "ongoing".

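### As worded, the by-arm AE tables count events that began before the single Day 1 dose

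*Protocol*

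**What the plan says.** Protocol section 8.3.7 gives the AE rule in two sentences. The first sets the scope: "All AEs will be listed by SOC, described and summarized by frequency tables". The second sets the count by treatment arm: "the percentage of patients having at least one occurrence of that event during the study", together with the total number of events. The synopsis repeats both. Neither refers to the time of dosing.

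Three places fix when an AE can first occur:

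- Section 7.1.3: "The reporting period for AEs is the period starting from the time of Informed Consent Form signature and lasting until Visit 5".
- Flow-chart footnote 8: "Starting at the screening visit, immediately after informed consent/assent, up to the follow up visit/telephone contact".
- Section 7.1.1: an untoward occurrence after consent is an AE "even if the subject was not administered the study drugs".

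The causality scale in section 7.1.2.2 gives onset before dosing as an example of an unrelated event, so such events are expected in the data.

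Section 8.3.7 does use the treatment-emergent concept, but for ECG only, where it asks for "frequencies of treatment emergent abnormalities". Laboratory and vital-sign data are summarized as change from baseline. The Safety population (section 8.2) requires intake of at least part of either study drug.

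**The concern.** Each child is dosed once, on Day 1. An AE that began before that dose says nothing about netupitant 1.33 versus 4 mg/kg (0.8 versus 2.4 mg/kg below 3 months), yet the stated rule places it in a dose column. Patients already exposed to chemotherapy are eligible, so the screening period can carry the aftermath of a previous cycle.

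Safety and tolerability are a secondary objective, this is planned as the first pediatric netupitant trial, and constipation and QT prolongation are named for special attention. The AE tables are also shown by strata. Because the screening limit doubles at age 2, a rule that includes pre-dose time can create an age difference that has nothing to do with the drug.

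**Working it through.** **1. The plan's own window.** Section 3.2 gives screening of up to 14 days (7 days below 2 years), follow-up contact 14 to 17 days after dosing, and a maximum duration of 31 days. 14 + 17 = 31 reproduces that maximum. Below 2 years it is 7 + 17 = 24 days.

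**2. Does any rule remove pre-dose events from the tables?**

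- The Safety population drops undosed children but keeps the pre-dose events of dosed children.
- Section 6.3.1 records examination findings as AEs only if found after first study drug intake. Section 6.3.4 does the same for laboratory abnormalities found after screening. Section 7.1.1 counts a condition present at study start only if it worsens.
- These rules narrow what is recorded. A symptom starting between consent and dosing, such as constipation or headache, is still recorded and tabulated.

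**3. Pre-dose share of the AE window at full-length screening:** share = pre / (pre + post).

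| Age | Follow-up 17 days | Follow-up 14 days |
|---|---|---|
| 2 years and older | 14/31 = 45% | 14/28 = 50% |
| Below 2 years | 7/24 = 29% | 7/21 = 33% |

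The age-class table plans 12 + 12 + 8 + 8 + 8 = 48 children below 2 years and 12 + 16 + 16 = 44 from 2 years. Pre-dose person-days are at most 48 × 7 + 44 × 14 = 952. The share is 952 / (952 + 92 × 17) = 38%, or 952 / (952 + 92 × 14) = 43%.

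These are shares of time. They become shares of events only if the event rate is the same before and after dosing.

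**4. How far the share falls under other assumptions.** The documents give no event rates or typical screening length.

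- Post-dose rate three times the pre-dose rate (assumed), full screening: 14/(14 + 3 × 17) = 22% to 14/(14 + 3 × 14) = 25% from age 2; 7/(7 + 51) = 12% to 7/(7 + 42) = 14% below 2 years.
- Screening on Day -1, taken as one day, equal rates: 1/18 = 6% to 1/15 = 7%.

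**5. Effect on incidence, upper-bound case.** With a constant hazard, full screening, 17 post-dose days and a true post-dose incidence of 10%, the tabulated value is 1 - 0.9^(window/17):

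- below 2 years: 1 - 0.9^(24/17) = 13.8%;
- from 2 years: 1 - 0.9^(31/17) = 17.5%.

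With 24 and 22 children per arm, that is 24 × 0.138 + 22 × 0.175 = 7.2 patients instead of 4.6 of 46. The gap between 13.8% and 17.5% comes from the window alone.

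**6. Effect on the dose contrast.** Let q be the probability of a pre-dose event, the same in both arms, and p the post-dose incidence, with the two independent. The tabulated incidence is 1 - (1 - q)(1 - p), so the difference between arms becomes (1 - q)(p2 - p1). From age 2, taking q = 1 - 0.9^(14/17) = 8.3% and true incidences of 10% and 20%:

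- tabulated values are 1 - 0.917 × 0.9 = 17.5% and 1 - 0.917 × 0.8 = 26.6%;
- the difference is 9.2 points instead of 10 (0.917 × 10), and the ratio is about 1.5 instead of 2.

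The contrast shrinks but does not change direction.

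**The case against.** **This is left to the SAP.** Section 8 says that it summarizes the methods and defers further detail to the SAP, which is not shown and may well tabulate treatment-emergent events. Had section 8.3.7 been silent, that would settle the matter. It is not silent: it names the set (all AEs) and the period (the study). A treatment-emergent filter would replace that set rather than add detail, so a SAP containing one would differ from the protocol text.

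**The study period is not defined in section 8.3.7.** True. The tabulation window is inferred from the AE reporting period. It is the literal reading, and no narrower period is offered for AEs.

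**The effect is small.** Much of this stands. Screening may be on Day -1. Emetogenic chemotherapy starts about an hour after dosing, so post-dose rates are probably higher. Some pre-dose findings are not recorded as AEs. Active infection, relevant Grade 3 or 4 laboratory values and recent vomiting are exclusions re-checked on Day 1, so some children with screening events are never dosed. The summaries are descriptive, and all AEs are listed, so nothing is lost for good.

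**Stronger readings.** A reader might infer three things that the documents do not support:

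- *That the tables are biased between doses.* In randomized classes, pre-dose events should fall on both arms alike. Below 12 months the first patients are assigned low dose then high dose, so balance is not assured there, but nothing points to a direction.
- *That about half of the tabulated AEs will be pre-dose.* That needs full-length screening for every child and equal event rates.
- *That the pre-dose window is open-ended*, because section 5.2.1 says "Informed consent/assent may also be collected before Visit 1". Flow-chart footnote 8 starts AE monitoring at the screening visit, and section 3.2 caps the study at 31 days. The 14- and 7-day limits are therefore used here.

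**Conclusion.** The point holds as a minor one. Sections 8.3.7, 7.1.1 and 7.1.3 together put pre-dose events of dosed children into the by-arm AE tables. The consequences are inflated descriptive incidence in both arms, some dilution of any dose contrast, and reduced comparability across the 2-year age boundary.

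The shares of 45-50% from age 2 and 29-33% below 2 years are upper bounds that rest on full-length screening and constant, equal rates before and after dosing. The actual share cannot be derived from the protocol and is likely to be clearly lower. No directional bias between doses is shown where patients are randomized.

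**What to change.** In section 8.3.7 and the matching synopsis entry, base the by-arm AE frequency tables on events with onset or worsening at or after the first intake of netupitant or palonosetron, up to Visit 5. List events between consent and dosing separately. Leave AE collection from consent as it is. The counted window is then at most 17 days at every age.

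The cost is wording plus a rule for events with onset on Day 1. Section 5.2.2 already requires dosing times to the minute. The rule also needs the AE onset time on that day, or a stated convention when it is missing.

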8.4 Interim Analysis

No interim analysis is planned for this study.

9 DATA SAFETY MONITORING BOARD

A Data Safety Monitoring Board (DSMB) will be convened for the evaluation of safety data during the study. The DSMB will not include employees of the Sponsor. Composition, role and responsibilities of the DSMB will be given in a separate document named DSMB charter. The purpose of the DSMB is to perform a qualitative safety assessment. Study data will be provided to the DSMB, as foreseen by the study design and at periodical intervals. Any additional information will be promptly made available by the Sponsor upon request of DSMB members.

The DSMB will have periodical face-to-face and/or telephone meetings, as appropriate and as foreseen by the study design, and a set of minutes will be issued after each meeting. A charter for the DSMB will be completed before patients enrollment begins.

10 ETHICAL AND REGULATORY CONSIDERATIONS

10.1 Ethical Considerations

The study will be performed in accordance with the principles contained in the Declaration of Helsinki [33] as amended by the World Medical Association in Fortaleza in 2013, and the ICH GCP guidelines as well as all local laws and regulations of the USA and other countries where the study is conducted, as applicable.

10.1.1 Laws and Regulations

This clinical study will be conducted in compliance with all international laws and regulations and national laws and regulations of the USA and other countries wherethe trial is performed, as applicable, as well as any applicable guidelines.

10.1.2 Patient's Information Sheet, Informed Consent Form and Assent Form

Before starting any study-specific evaluations or procedures, parent(s)/legal guardian(s) of all patients invited to participate in the study and patients of appropriate age and intellectual maturity as defined by local laws and regulations must be given written and verbal information about the aims, methods, anticipated benefits and potential hazards of the study. Furthermore, the patients and their parent(s)/legal guardian(s) must be notified that participation is voluntary, and that the patient is free to withdraw from the study at any time without any disadvantages for the patient's subsequent care. The parent(s)/legal guardian(s) is/are also free to withdraw their child from the study at any time without any disadvantages for the child's subsequent care.

In addition, parent(s)/legal guardian(s) will be given the Information for Parents and Informed Consent Form in native language expressed in clear, concise and lay language for review and consideration. As required by local laws and regulations, all patients of appropriate age and intellectual maturity will be given the Children's Information Sheet and Assent Form explaining the study in age-appropriate terms.

Information for Parents and Informed Consent Form as well as the Children's Information Sheet and Assent Form will tell potential patients and their parent(s)/legal guardian(s) about the nature of the drugs, its efficacy and safety profile, the route of administration, and the available clinical experiences in humans. It will also outline the steps of the protocol as they will apply to the individual including the number of visits, the number of procedures and types of assessments/measurements to be performed so that the individual has a clear picture of the risks, inconveniences and benefits that may accrue.

The patients and their parent(s)/legal guardian(s) must also know that patient's personal medical records may be reviewed in strict confidence by the Sponsor's staff or representatives and by Regulatory Authorities and Independent Ethics Committees(IEC)/Institutional Review Board (IRB) and that personal information about

patients will be held on a confidential database. Conditions for ensuring the anonymity of data and the security and confidentiality of the database should be explained.

Both the Informed Consent Form and the assent form must be previously approved by relevant IEC(s)/IRB and may further be updated as new important information becomes available that may affect patient's or parent(s)/legal guardian(s) willingness to participate or continue in the trial.

Written Informed Consent Form signed by the parent(s)/legal guardian(s) must be obtained prior to enrollment of all pediatric patients and the signed assent form should be obtained from all patients of appropriate age and intellectual maturity in compliance with local laws and regulations.

Two copies of the Informed Consent Form and Assent Form shall be signed. The Investigator shall provide one signed copy of the Informed Consent Form to the parent(s)/legal guardian(s) and one copy of the assent form to the child (if applicable), and will keep the second copy of the original signed forms in the Investigator's study file.

10.1.3 Protocol Amendments

Changes to the protocol may only be made by means of a written amendment, which has to be approved and signed by the authorized individuals of the Sponsor and by the Investigator. The study code, the title of the study, the progressive number and the date of the amendment must be recorded on the first page of the document. Exhaustive justifications that motivate the amendment to the protocol should clearly be addressed in the document. All protocol amendments must be submitted to the EC/IRB for review and approval (as well as to Competent Authorities, where applicable for authorization) unless it covers administrative issues only. In this case, the EC/IRB and Competent Authorities will be notified of the amendment for information purposes only, as applicable.

10.1.4 Protocol Deviations

The Investigator has to conduct the study in accordance with the approved current protocol and will not be allowed to make any changes with the only exception when immediate changes are necessary to protect the safety, rights, and welfare of the patient.

In order to obtain interpretable results, neither the Investigator nor the Sponsor/CROs will alter the study conditions agreed upon and set out in this protocol.

In the event that an isolated, unforeseen instance resulting in a protocol deviation occurs, the Investigator is to document this deviation and notify it to the clinical CRO as soon as possible, in writing. In no instance should this increase the patient's risk or affect the validity of the study data.

